Study Protocol and Statistical Analysis Plan

Study Title:

Comparative Evaluation of SmartMouth Clinical DDS Advanced Oral Rinse and Chlorhexidine Mouth Rinse

Date:

7-13-2015

Introduction:

The primary etiology for dental caries, gingivitis, and periodontal disease is the formation of bacterial colonies on the tooth surface. An inflammatory process follows the accumulation of dental plaque resulting in gingivitis. Many studies have demonstrated that plaque-induced gingivitis can be reversed following complete plaque removal. Patients are instructed by oral health professionals to regularly and thoroughly remove plaque using a daily oral hygiene regimen. Many patients demonstrate poor compliance, possibly due to lack of motivation, dexterity, or skill. An antimicrobial mouth rinse, when used as an adjunct to daily oral hygiene routine, can be beneficial to patients by reducing plaque accumulation and gingival inflammation.

Mouth rinses with 0.2% chlorhexidine gluconate are used commonly in Europe. Numerous studies have demonstrated the antiplaque and anti-gingivitis effectiveness of this rinse. Side effects associated with this mouth rinse include tooth staining, calculus formation, and altered taste sensation. Studies have also been conducted with 0.12% chlorhexidine. These trials found the antiplaque and anti-gingivitis effectiveness is comparable to the 0.2% solution, but with diminished side effects. The 0.12% chlorhexidine mouth rinse (Peridex®) is widely used on a prescription basis in the United States.

Clinical trials have confirmed the efficacy of cetylpyridinium chloride (CPC) mouthrinses, but there is limited data comparing CPC to other antimicrobial ingredients. CPC rinses are not associated with side effects such as staining or taste alteration, and its use is well tolerated by patients. SmartMouth Clinical DDS Advanced Oral Rinse (a.k.a. SmartMouth Advanced Clinical Formula) (Triumph Pharmaceuticals, Inc., St. Louis, MO) is an over-the-counter mouth rinse formulated to reduce plaque and gingivitis and to provide long term fresh breath through the elimination and prevention of bad breath sulfur gases (Volatile Sulfur Compounds or VSC) utilizing zinc-ion technology. The active ingredient in SmartMouth Clinical DDS Advanced Oral Rinse is 0.05% cetylpyridinium chloride (CPC).

The aim of this six-week double-blind, placebo-controlled clinical trial was to provide evidence of the clinical efficacy of SmartMouth Clinical DDS Advanced Oral Rinse (SM) in comparison with the efficacy of 0.12% chlorhexidine rinse (CHX) and a placebo rinse (PL). The outcomes included measures of plaque, gingivitis, tooth staining, calculus formation, patient compliance, and taste perception.

Materials and Methods:

A six-week, double-blinded, clinical study will be conducted on 80 subjects diagnosed with plaque induced gingivitis and/or chronic periodontitis. The study will take place at two centers: Saint Louis University Center for Advanced Dental Education (Site 1) and Southern Illinois University School of Dental Medicine (Site 2). The study was approved by the Institutional Review Boards (IRB #25867) at Saint Louis University and Southern Illinois University Edwardsville.

Subjects who sign the informed consent and medical history forms and meet the preliminary entrance criteria will be examined at baseline (visit 1). All participants will be informed of the nature of the study, its purpose, and any possible risks. Subjects will be informed as to the length of the study and the specific procedures that would be performed. Subjects will be informed that this was a voluntary study and that they are free to withdraw from the study at any time.

Gingival index (GI) will be measured using the Loe and Silness method.²⁴ The gingiva will be scored at six sites of each tooth (distobuccal, buccal, mesiobuccal, distolingual, lingual, mesiolingual) and given a score from 0 – 3. By adding the scores and dividing by the total number of sites, the GI for the patient will be obtained.

Sites with GI scores of 2 or 3 will be counted as bleeding. A whole mouth total Bleeding Score (BS) will be calculated by summing the number of bleeding sites and dividing by the number of teeth.

Extrinsic tooth stain will be scored on the facial surfaces of the eight incisor teeth using a modification of the Lobene tooth stain index (TSI).²³ Each incisor will be scored for stain area on a scale of 0-3. The sum of the stain scores for the subject will be used as that subject's stain score.

Supragingival calculus on the lingual surfaces of the six mandibular anterior teeth will be scored using the Volpe-Manhold calculus index (CI).³⁶ Supragingival calculus height in three defined planes on the lingual surface of each tooth will be measured using a periodontal probe. The measurements will be added and a mean subject score calculated.

Plaque will be scored based on the Turesky modification of the Quigley—Hein Plaque Index (PI).³³ A score of 0 – 5 will be assigned to six sites of each tooth (distobuccal, buccal, mesiobuccal, distolingual, lingual, mesiolingual) following the use of a disclosing solution. The Plaque Index for the entire mouth will be determined by dividing the total score by the number of surfaces examined.

Teeth with gross caries and third molars will not be scored. A complete periodontal examination will be performed for all subjects that meet the inclusion criteria. A panoramic radiograph will be taken for all subjects who do not have full mouth radiographs within the last year. Safety assessments will be made at each measurement visit.

Visit 2 will occur within four weeks of Visit 1. For this relatively small clinical study for which there are two centers and three treatments, subjects will be assigned treatments through the process of minimization to assure a balance in the number of subjects in each treatment group: Group 1 SM, Group 2 CHX or Group 3 PL. PL will be identical to SM, except it will not contain cetylpyridinium chloride, zinc chloride and sodium chlorite. Each group will consist of approximately 25 subjects. All subjects will be given a complete dental prophylaxis to remove plaque, calculus, and stain. Written and verbal oral hygiene instructions will be given that will includ a regular regimen of brushing twice daily and flossing daily. All subjects will be assigned a commercially available ADA accepted toothbrush and dental floss. They will be given a three-

week supply of the assigned mouth rinse with written and verbal instructions for use. Subjects will be instructed not to have their teeth professionally cleaned prior to study completion.

All mouth rinses will be in a plain package and dispensed by the faculty investigators. The package will be labeled with a code to indicate the product. Only the faculty investigators will have access to the code information. Group assignment will be performed by one of the investigators who will use the process of minimization and will not be aware of the periodontal health of subjects. Directions for use are contained in the package. The examiners will not see the product. The examiners will give instructions for mouth rinse use, but they will not be aware which rinse the subjects are using. Each product will contain two solutions which are mixed prior to use.

Subjects will be examined again at visit 3, three weeks after visit 2. All clinical measurements will be repeated. Each subject will return the unused rinse. Additional rinse will be given to each subject after visit 3 for use until the final visit. Compliance will be determined by regulating the amount of rinse dispensed on a 3 week basis and by the measurement of any unused rinse (compliance defined as percentage of product used).

Subjects will be examined again at visit 4, three weeks after visit 3. Clinical measurements will be repeated. Each subject will return the unused rinse. Compliance will be determined by the measurement of any unused rinse at the end of the study. Subjects will be given a Taste Perception Survey to answer questions about their experience with the mouth rinse.

Following the study, the subjects will be treated by their provider's discretion. Subjects can withdraw from the clinic trial at any time without providing reason. The investigators can also withdraw subjects at any time due to protocol irregularity. All instances of withdraw will be documented.

Intra-Examiner Calibration

Intra-examiner calibration will be completed prior to beginning the study. Three examiners ([name]) will make original and repeat determinations of values for four teeth in ten subjects for each of four indices. A kappa value will be determined for each original and repeat determination, and the average kappa value will be determined for the four teeth for each index for each examiner. For an examiner to be considered calibrated, average kappa values for each index have to be between 0.81 and 1 (almost perfect agreement).

Data Analysis

The primary outcome measures are gingivitis and plaque. Secondary outcome measures are tooth discoloration, taste perception, malodor and calculus. For each outcome measure, a single value will be calculated for each subject—that is, the subject is the unit of measurement for analyses.

Analyses will be based on intention to treat (with randomized intervention). Sensitivity analyses will be based on as treated analyses. To test for differences among and between treatments, we will

use repeated measures analysis of variance (ANOVA) with treatment and location as the between-group factors and one within-subject (repeated-measures) factor with 2 levels: (1) measurements at visit 3 and (2) measurements at visit 4. For these analyses, we will use multivariate analysis of variance (MANOVA), which does not require the assumptions of compound symmetry (homogeneous pooled within-group variances and across-subjects covariances) and sphericity (orthogonal components). Post-hoc testing will be performed with the Tukey honestly significant difference ([HSD] test.

Sample-size calculation and power analysis (treatment effect of Smart Mouth ACF): One goal of the proposed study is to test the null hypothesis that the mean gingival score for Smart Mouth ACF is equal to the mean gingival score for the placebo (control). With alpha (the criterion for significance) set at 0.05, a 2-tailed test (which means that an effect in either direction will be interpreted), and a sample size of 20 and 20 for the two groups, the study will have a power of 99.9% to yield a statistically significant result. This computation is based on data from Ayad et al (2011), with the assumption that the mean difference is 0.44 (corresponding to means of 2.03 versus 1.59) and a common within-group standard deviation of 0.27 (based on SD estimates of 0.22 and 0.31). We assume that this effect size is reasonable, in the sense that an effect of this magnitude is anticipated in this field of research. We could report an observed difference of 0.44 with a 95.0% confidence interval of 0.27 to 0.61. Based on plaque scores given in Ayad et al (2011) and a sample size of 20 in each group, we would have a power >99.9% to demonstrate a treatment effect for Smart Mouth ACF. Our intent is to enroll 25 subjects into each group. Our sample-size calculations assume a 20% dropout rate. We, however, anticipate that the dropout rate will be less than 10%.

Equivalence of Smart Mouth ACF with 0.12% chlorhexidine. We will have power of 82% to demonstrate that the mean gingivitis score for Smart Mouth ACF is the same (neither lower nor higher) than the mean for .12% chlorhexidine. This assumes that the mean values for the two treatments are equal, with a common within-group standard deviation of 0.25, that a difference of .20 points or less is unimportant, that the sample size in the two groups will be 21 and 21, and that alpha (1 tailed) is set at .05. For this calculation, we used standard deviations from Ayad et al (2011). Formally, the null hypothesis is that the mean for Smart Mouth ACF is 0.20 points lower or higher than the mean for .12% chlorhexidine, and the study has power of 81.7% to reject this null. Equivalently, the likelihood is 81.7% that the 95.0% confidence interval for the mean difference will exclude a difference of 0.20 points in either direction.

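### Minimization is specified only to equalize group numbers: no random element, tie rule or prognostic factor is stated, and the model does not adjust for baseline

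*Combined protocol and SAP*

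**What the plan says.** The allocation method is described in Materials and Methods, in the text on visit 2 and on packaging and assignment. The stated purpose is: "subjects will be assigned treatments through the process of minimization to assure a balance in the number of subjects in each treatment group". The same sentence opens by giving the setting as a reason: "For this relatively small clinical study for which there are two centers and three treatments". Center is thus mentioned, but neither it nor anything else is named as a minimization factor.

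On who does it: "Group assignment will be performed by one of the investigators who will use the process of minimization". The sentence goes on to say that this person "will use the process of minimization and will not be aware of the periodontal health of subjects". On the product: "All mouth rinses will be in a plain package and dispensed by the faculty investigators", and "Only the faculty investigators will have access to the code information". The examiners do not see the product and do not know which rinse a subject uses.

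The population is "80 subjects diagnosed with plaque induced gingivitis and/or chronic periodontitis", so disease severity is mixed. GI, plaque and the periodontal examination belong to visit 1; assignment follows at visit 2, up to four weeks later.

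The Data Analysis section states "Analyses will be based on intention to treat (with randomized intervention"). Its model has treatment and location as between-group factors and visits 3 and 4 as the repeated measure. Visit-1 values do not enter it. Nowhere do the documents give an assignment probability, a tie rule, a software tool or a concealment step.

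**The concern.** Two things are at stake.

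The first is predictability. Minimization with no random component fixes the next assignment whenever one arm is smallest. Anyone who knows the running counts then knows the next arm. If that person could also influence who enters, or in what order, the arms could differ systematically. The plan relies on random assignment for its intention-to-treat analysis but describes no random step.

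The second is precision. The main attraction of minimization in a small trial is balance on variables that predict the outcome. Here the stated target is head count alone. Because the assigner is masked to periodontal health, that person cannot balance GI or diagnosis by hand. The model does not use baseline either, so a chance difference between arms is neither prevented by design nor removed in analysis. This matters most for the comparison with chlorhexidine, where the Data Analysis section treats a GI difference of 0.20 or less as unimportant.

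**Working it through.** The documents give no figure for predictability or balance, so there is none to reproduce on this exact point. The planning inputs used below do reproduce.

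**Inputs**
- SD 0.27 (sample-size paragraph, Data Analysis): √((0.22² + 0.31²)/2) = 0.269.
- SD 0.25 and margin 0.20 (equivalence paragraph).
- 25 per group: 20/(1 − 0.20) = 25.
- Power with 20 per group, difference 0.44, SD 0.27, two-sided 0.05: 99.93% (normal) or 99.89% (t), against 99.9% stated.
- Three arms, two centers, total 75 (3 × 25) or 80 (Materials and Methods).

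**Predictability under strict count balancing with random ties**

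Each run of three assignments has best-guess probabilities 1/3, 1/2 and 1.
- Forced: 1 in 3 = 33.3%.
- Guessed correctly: (1/3 + 1/2 + 1)/3 = 11/18 = 61.1%.
- With 80 subjects there are 26 complete runs, so 26/80 = 32.5% are forced. Simulation with counts kept within two centers of equal expected enrollment gives 32.5% forced and 60.6% guessable.

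The text fits other procedures too. A fixed tie rule would make 100% of assignments predictable; an unstated random element would make 0% certain. Under simple randomization 33% would be guessed correctly.

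**Adding a random element** (simulation, 1,000 trials per setting, count-only balancing, overall or within center, 75 or 80 subjects). The probability of choosing a least-filled arm is an assumption.

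| Probability | Certain | Guessed correctly | Mean gap, largest − smallest arm |
|---|---|---|---|
| 1.0 | about 33% | about 61% | 0 to 1.1 |
| 0.9 | 0% | 58% | 0.5 to 1.4 |
| 0.8 | 0% | 55% | 1.0 to 1.9 |
| 0.7 | 0% | 50–51% | 1.8 to 2.9 |

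These figures were not computed for minimization on three factors.

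**Chance imbalance in baseline GI**, assuming the planning SDs apply at visit 1
- SE = SD × √(2/25): 0.25 × 0.2828 = 0.0707; 0.27 × 0.2828 = 0.0764.
- 95% range = ±1.96 × SE: ±0.139 to ±0.150, or ±0.55 SD.
- Average absolute difference = 0.798 × SE: 0.056 to 0.061, about 0.06.

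**Carry-over to the outcome**

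With equal SDs at baseline and follow-up, the expected carry-over is the baseline difference times their correlation r. The documents give no r. At an assumed r = 0.5, a 0.15 difference carries 0.15 × 0.5 = 0.075, and the average difference carries 0.06 × 0.5 = 0.03. Over the full range r = 0 to 1, a 0.15 difference carries 0 to 0.15. All subjects also have a full prophylaxis at visit 2, which may lower r.

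**The case against.** The strongest reply is that this is a gap in the description, not a shown defect. Minimization is often run with a random element, and the plan calls the intervention randomized. A reader might infer that a third of assignments are predictable, or that the trial is not randomized. The documents support neither, because silence on the random element does not show that there is none. That part of the objection stands, and the 33% and 61% must stay conditional.

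The plan also has real safeguards. The assigner does not know periodontal health, the examiners do not see the product, and consent and the baseline examination come before allocation. A reader might infer that the assigner holds the product code and can steer subjects. The text gives the code to the faculty investigators and the assignment to one of the investigators, without saying that this is a faculty investigator. No documented route joins knowledge of the next arm to knowledge of prognosis. This stands too. What remains is that masking covers only the assigner and the examiners. The documents do not say whether code-holders influence enrollment or the timing of visit 2 within its four-week window, so selection bias is limited but not excluded.

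Center may be an intended factor, since the two centers are cited as part of the reason for minimization and location is in the model. Group size is therefore the only stated target, not necessarily the only one used.

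Finally, a reader might set ±0.15 beside the 0.20 margin and infer bias of that size. That is not supported. It is a 95% extreme under an assumed baseline SD, simple randomization would produce it as well, and chance imbalance is already in the standard error. Baseline adjustment alone would deal with much of it. That is right as far as precision goes, but the plan has no such adjustment, and adjustment does nothing about predictability.

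**Conclusion.** The point holds as a weakness in the allocation method that is cheap to improve, not as proof of bias. Equal group numbers are the only stated target; no random element or tie rule is given; and visit-1 GI and diagnosis, available before allocation, are neither balanced by design nor in the model.

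The forced and guessable shares above apply only if counts are strictly balanced with random ties; otherwise certainty could lie anywhere from 0% to 100%. The imbalance range rests on the planning SDs holding at visit 1 and on 25 per group. It measures lost precision, not bias, and only the part given by the baseline–outcome correlation reaches the result.

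**What to change.** - Run the minimization by computer with a random element, for example the minimizing arm with probability 0.8, and state the tie rule.
- Use center, visit-1 GI (high/low) and diagnosis as factors. Enter GI and diagnosis as codes so that the assigner stays masked to periodontal health.
- Register each subject irrevocably before the assignment is shown, and state who runs the system and who can see the running counts.
- Put the same factors in the analysis model, with baseline GI as a covariate. Balancing on GI and diagnosis while leaving them out of the model would make the standard errors too wide and forfeit the gain. Location is already there.

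**Cost.** A spreadsheet or free software, two coded items already collected at visit 1, and a few sentences in Materials and Methods and Data Analysis. Group sizes would differ by about 1 to 2 subjects on average at probability 0.8. That figure is for count-only balancing and should be rechecked by simulation for the three-factor scheme, along with the guess rate.

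### Taste perception is a secondary outcome but is surveyed only at visit 4, so early leavers give no taste data and a real taste difference may be understated

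*Combined protocol and SAP*

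**What the plan says.** Data Analysis states: "Secondary outcome measures are tooth discoloration, taste perception, malodor and calculus". Taste is also among the outcomes listed in the trial's aim.

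The survey is mentioned once, in the Materials and Methods paragraph on the final visit: "Subjects will be given a Taste Perception Survey to answer questions about their experience with the mouth rinse". That visit falls six weeks after rinsing starts: "Subjects will be examined again at visit 4, three weeks after visit 3", and visit 3 is itself three weeks after visit 2, when the rinse is dispensed. The visit 3 paragraph reads: "Subjects will be examined again at visit 3, three weeks after visit 2. All clinical measurements will be repeated". It does not name the survey, and a questionnaire is not naturally read as a clinical measurement.

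On leaving the study, Materials and Methods says: "Subjects can withdraw from the clinic trial at any time without providing reason". It adds: "All instances of withdraw will be documented". No exit visit or exit survey is described.

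On the amount of loss, Data Analysis says: "Our sample-size calculations assume a 20% dropout rate". It then anticipates less than 10%. Analysis is by intention to treat, and no method for missing data is given. The one model described is a repeated-measures analysis with two levels, visit 3 and visit 4.

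On taste itself, the Introduction says of the 0.2% chlorhexidine rinse: "Side effects associated with this mouth rinse include tooth staining, calculus formation, and altered taste sensation". It describes side effects as diminished at 0.12%, the strength used in this trial, and says that rinses with cetylpyridinium chloride (CPC), the active ingredient of SM, are not linked to altered taste.

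**The concern.** A question asked only at the end reaches only those who are still there. Disliking a rinse is a plausible reason to leave a six-week rinsing study, and the Introduction gives some ground for expecting more dislike in one arm. If such subjects leave, the week 6 survey over-represents people who tolerated their rinse, most of all in the arm that tastes worse. The trial could then report a smaller taste difference between CHX and SM than exists, on an outcome that it chose to measure.

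Two gaps in the plan make this harder to handle. Intention to treat cannot be followed fully for taste, because a subject lost before week 6 has no taste value at all. And the planned two-visit model cannot be applied to an outcome measured once, so the taste analysis is in effect unspecified.

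**Working it through.** **The plan's own figures.** Data Analysis gives 20 completers per group, 20% dropout and 25 enrolled: 20 / (1 − 0.20) = 25, which agrees. Without an earlier survey, the number per arm with no taste value is 25 × 0.20 = 5 at the planning rate, and fewer than 25 × 0.10 = 2.5 at the anticipated rate. The documents give no dropout by arm, no expected taste result and no link between taste and withdrawal. Everything below on those points is an assumption.

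**Proportions.** Assume 25 per arm, with 10/25 = 40% on CHX and 3/25 = 12% on SM finding the taste bad, and no SM withdrawals.

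| Taste-related CHX withdrawals before visit 4 | CHX observed | SM observed | Difference |
|---|---|---|---|
| 0 | 10/25 = 40% | 12% | 28 points |
| 2 (8%, within the anticipated rate) | 8/23 = 34.8% | 12% | 22.8 points |
| 5 (20%, planning rate) | 5/20 = 25% | 12% | 13 points |

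For scale, the standard error of the full difference is √(0.40 × 0.60/25 + 0.12 × 0.88/25) = 0.118, about 12 points. The shift in the middle row, 28 − 22.8 = 5.2 points, is under half of that. The last row is an upper scenario: every CHX withdrawal is due to taste and SM loses nobody.

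**A continuous score.** Take taste in SD units, and let d be an arm's dropout and ρ the correlation between bad taste and the tendency to leave. Under a normal model, the mean among those who remain shifts upward by ρ × φ(z_d) / (1 − d), where z_d is the normal quantile at d and φ is the normal density.

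- d = 0.10: 0.1755/0.90 = 0.195 at ρ = 1, and 0.097 at ρ = 0.5.
- d = 0.20: 0.2800/0.80 = 0.350 at ρ = 1, and 0.175 at ρ = 0.5.

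The bias in favour of the worse-tasting arm is its shift minus that of the other arm:

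| Dropout, worse arm vs other arm | ρ = 0 | ρ = 0.5 | ρ = 1 |
|---|---|---|---|
| 10% vs 0% | 0 | 0.097 SD | 0.195 SD |
| 20% vs 10% | 0 | 0.077 SD | 0.155 SD |
| 20% vs 0% | 0 | 0.175 SD | 0.350 SD |
| equal dropout, equal ρ | 0 | 0 | 0 |

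**One tolerance threshold for both arms.** If subjects in both arms leave at the same level of dislike, the other arm's dropout follows from the true difference. For an assumed true difference of 0.5 SD:

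- 10% dropout in the worse arm implies 3.7% in the other. The observed difference is 0.445 SD (ρ = 0.5) or 0.39 SD (ρ = 1), a loss of 11% or 22%.
- 20% implies 9.0%. The observed difference is 0.414 SD or 0.328 SD, a loss of 17% or 34%.

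The difference shrinks in every case and does not change sign. Assumed true differences of 0.3 and 0.8 SD also show no change of sign, and over all three the loss runs from 9% to 37%.

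**The case against.** The strongest reply is that the bias depends on two things the documents do not show: that people leave because of taste, and that they do so unequally between arms. That stands. With unrelated dropout, or equal dropout with equal dependence on taste, the bias is zero. A reader might infer that the comparison is biased as designed; the documents support only that it may be.

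Second, the sentence listing altered taste is about the 0.2% rinse, and the Introduction calls side effects diminished at 0.12%. That stands too. It makes CHX the plausible worse-tasting arm but does not establish it.

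Third, stopping the rinse is not leaving the study. A subject who stops rinsing but attends visit 4 still receives the survey and stays in the intention-to-treat analysis, and the unused rinse measured at visits 3 and 4 would show the avoidance. So it is not the case that anyone who gives up a rinse over taste goes unheard.

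Fourth, the right to leave without explanation does not stop staff from noting a reason that is offered, and withdrawals are documented. Safety assessments at measurement visits might also pick up complaints. This is partly right: neither provision requires a reason or a taste answer.

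Fifth, a reader might infer that no analysis can deal with the loss. In the example, counting the five withdrawals as bad taste gives (5 + 5)/25 = 40% and restores the 28 points. A worst-score analysis cannot say what those subjects thought, but it can bound the effect.

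Finally, taste is secondary, and if CHX tastes worse the error works against SM's expected advantage. That limits the stakes. It does not remove the risk of missing a real difference.

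**Conclusion.** The gap is real: taste is a secondary outcome with one scheduled collection, at week 6, and subjects who leave earlier contribute nothing to it. Whether this biases the comparison of SM and CHX is conditional on withdrawal being taste-related and heavier in the worse-tasting arm. If so, the taste difference is understated. At the anticipated dropout the effect is modest: about 5 of 28 points on the assumed rates, or at most about 0.2 SD (10% against 0%, with leaving wholly determined by taste). The fall to 13 points and the 0.35 SD figure are upper scenarios at the planning dropout.

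A reader might infer that the ranking of the rinses could flip. Under a common tolerance threshold it does not. A flip would need a true difference smaller than the bias, with a split of dropout between arms more extreme than that difference would itself produce, and nothing in the documents points to this. The primary outcomes, gingivitis and plaque, are not affected by this point. It is a cheap improvement and not a flaw in the trial's main conclusions.

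**What to change.** 1. Give the same Taste Perception Survey at visit 3 as well as visit 4. Every remaining subject already attends visit 3, and this supplies both time points that the planned model uses.
2. Offer the survey at withdrawal where contact occurs. Keep it voluntary, so that the right to leave without a reason is untouched.
3. State the taste analysis: by assigned group, using visit 3 and visit 4 data, with a method that keeps subjects who have visit 3 only. A mixed model would do this if the survey yields a score. The multivariate form named in Data Analysis normally drops anyone with a missing visit, which would discard the added answers.
4. Report survey completeness by arm and visit.
5. Add a sensitivity analysis that gives withdrawals without any survey the worst score.
6. Use a last-available-survey summary only as a supporting view, because it mixes three-week and six-week exposure.

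The cost is a few minutes per subject and some added analysis text. Subjects who leave before visit 3 may still be missed, and some will decline the survey on leaving, so items 4 and 5 are needed even with the extra survey.

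### Investigators may withdraw subjects for an undefined protocol irregularity, with no stated follow-up afterwards, so the declared intention-to-treat analysis is not secured

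*Combined protocol and SAP*

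**What the plan says.** The withdrawal paragraph of Materials and Methods has three parts. Subjects may leave: "Subjects can withdraw from the clinic trial at any time without providing reason". Investigators may remove them: "The investigators can also withdraw subjects at any time due to protocol irregularity". The only stated consequence is a record: "All instances of withdraw will be documented". Because the first of these concerns leaving the trial, the natural reading of the second is removal from the trial, not only from the rinse.

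Data Analysis then states: "Analyses will be based on intention to treat (with randomized intervention"). It adds: "Sensitivity analyses will be based on as treated analyses". The model has "one within-subject (repeated-measures) factor with 2 levels: (1) measurements at visit 3 and (2) measurements at visit 4", and the method is given as: "For these analyses, we will use multivariate analysis of variance (MANOVA").

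On data collection, Materials and Methods says: "Safety assessments will be made at each measurement visit". All clinical measurements are repeated at visit 3 and clinical measurements again at visit 4. The taste survey appears only at visit 4. Access to the product code is limited to the faculty investigators, who also dispense the rinses; the examiners are kept unaware of the product.

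**The concern.** Intention to treat needs two things: subjects are analysed in the assigned group, and their outcomes are obtained whether or not they followed the protocol. The plan states the first and makes no provision for the second. It also gives investigators discretion, after assignment, to take subjects out on a ground it never defines.

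If those removed differ from those kept, and differ by arm, the treatment comparison is biased. Low rinse use, or a professional cleaning during the study, are plausible examples of an irregularity, although the plan lists neither as one. Rinse use could well differ by arm, since the Introduction associates staining, calculus and altered taste with chlorhexidine and says that CPC rinses do not cause staining or taste change. The plan also does not require the investigator who decides on a withdrawal to be blind to the product code.

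At stake are the size of the SM-placebo estimate, the SM-chlorhexidine equivalence comparison, and taste as a secondary outcome.

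**Working it through.** **Tracing a withdrawn subject through the plan**

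| Point of withdrawal | Scores held | Place in a standard visit 3 and 4 MANOVA |
|---|---|---|
| Before visit 3 | Baseline only | Dropped |
| Between visits 3 and 4 | Baseline and visit 3 (indices, safety); no taste survey | Dropped, because the visit 4 value is missing |
| At or after visit 4 | All | Kept |

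This assumes that withdrawn subjects are not examined again, on which the plan is silent. No method for a missing visit is given. The as-treated sensitivity analysis regroups subjects by what they received; it cannot supply scores that were never taken.

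**Is it a power problem?** Inputs from the sample-size paragraph of Data Analysis: difference 0.44, SD 0.27, 20 per group, two-sided alpha 0.05.
- Dropout: 25 × (1 − 0.20) = 20 per group, as stated.
- SE = 0.27 × √(2/20) = 0.0854; noncentrality = 0.44/0.0854 = 5.15; noncentral t on 38 df gives 99.89%. The plan's 99.9% is reproduced.
- With 18 per group: 99.7%. With 15 per group: 99.0%.

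Losing subjects hardly moves power for SM against placebo. The issue is bias.

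**Size of a possible bias (illustration only).** Let a fraction w of one arm be removed, and let those subjects' GI be g points worse than that of the subjects retained.
- Intention-to-treat mean = (1 − w) × m + w × (m + g) = m + w × g, where m is the mean of those retained.
- The analysed mean is m, so the arm looks better by w × g.

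| w | g = 0.22 | g = 0.44 |
|---|---|---|
| 5% | 0.011 | 0.022 |
| 10% | 0.022 | 0.044 |
| 20% | 0.044 | 0.088 |

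The value 0.44 is the plan's SM-placebo difference, so g = 0.44 in the SM arm means that the removed subjects would have scored like placebo; 0.22 is half of it. The 20% is the plan's dropout allowance and 10% the level it expects to stay below. Both are all-cause dropout rates, used here only as a scale. The 5% is assumed.

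For the SM arm, the extreme corner means reporting 0.44 where intention to treat would give 0.44 − 0.088 = 0.352. At 0.352 with 20 per group, noncentrality is 0.352/0.0854 = 4.12 and power is still 98.0%. Against the 0.20 equivalence margin, 0.088 is 44% (0.088/0.20) and 0.011 is 5.5% (0.011/0.20).

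**The case against.** The strongest reply is that the plan is silent, not wrong. The withdrawal power is permissive, and intention to treat concerns analysis by assigned group, so the two can coexist. A reader might infer that the passages contradict each other, or that withdrawn subjects may not be examined again. The documents say neither, and this part of the objection stands.

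A reader might also infer that the rule targets subjects who use the rinse poorly. The text does not support that. Compliance is listed as an outcome and measured as a percentage of product used, with no threshold and no consequence. The planned as-treated analysis suggests that subjects who depart from assignment stay in the data. An irregularity could equally be an eligibility or consent error.

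Nor would all efficacy and side-effect data be lost. A subject withdrawn after visit 3 already has that visit's indices and safety assessment; only the taste survey is wholly missing.

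The 0.088 is a one-arm worst case. It takes all removals from one arm, with no benefit in any removed subject and no visit 3 score used. Removals from chlorhexidine alone would leave the SM-placebo difference unchanged, and the plan gives no chlorhexidine-placebo effect from which to scale g in that arm. Equal removals with equal g in SM and chlorhexidine would cancel in their difference. Reading 44% of the margin as an expected bias is therefore not supported.

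The core is not answered. The ground is open-ended, nothing states what happens to the subject's remaining visits, and the named method in its standard form has no place for a subject with one visit.

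**Conclusion.** The point holds as a weakness in the design: a plan that declares intention to treat allows discretionary exclusion after assignment and does not say how the outcomes of those subjects are obtained. It should be changed; confidence is medium.

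The possible shift in one arm's mean GI is 0.011 to 0.088, resting on assumed removal rates of 5% to 20% and an assumed deficit of 0.22 to 0.44. The documents give no investigator-withdrawal rate and no outcome for such subjects, so this is a scale and not a forecast. A shift of this size would seldom change the SM-placebo test. It matters for the reported estimate and for the comparison against a 0.20 margin. That the analysis becomes one of completers depends on withdrawn subjects not being seen again and on the standard form of MANOVA; the plan rules out neither.

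**What to change.** Reword the withdrawal paragraph of Materials and Methods:

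- A protocol irregularity is recorded but does not by itself end data collection.
- Subjects who still consent, and for whom continued examination raises no safety concern, attend the already planned visits 3 and 4 for the indices, the safety assessment and, at visit 4, the taste survey.
- They are analysed in the assigned group. Irregularities are addressed in the as-treated sensitivity analysis that Data Analysis already names.
- Any investigator withdrawal is decided without knowledge of the product code.
- A reason is invited but not required, which keeps the subject's stated right to leave without giving one.

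When rinse use should stop is left to the protocol.

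Cost: a change of wording and a short entry on the withdrawal record. The visits are already in the schedule, though some that would have been dropped are now kept. The intention-to-treat effect may come out slightly smaller. The change has to be in place before withdrawals occur, because a missed examination cannot be recovered later.
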